5.3. Lifestyle Considerations

5.3.1. Meals and Dietary Restrictions

- During the in-house stay(s), the subjects may only consume food and beverages provided by the study site. The diet provided (maximum of 4 meals per day) will consider the imposed restrictions. On Days 1 to 7 of both study periods, subjects will receive standardized meals, served at customary times.
- Further dietary restrictions to be observed are displayed in [Table 5](#).

5.3.2. Caffeine, Alcohol, and Tobacco

- Restrictions on caffeine, alcohol, and tobacco are described in [Table 5](#).

5.3.3. Activity

- Restrictions on activity are described in [Table 5](#).

5.3.4. Other Restrictions

- Other restrictions are described in [Table 5](#).

Table 5: Restrictions

| What? | Restriction |
|---|---|
| Dietary restrictions | |
| Caffeine- or xanthine-containing food and beverages (e.g., coffee, tea, cola, chocolate, and energy drinks) | Not allowed during both treatment periods (Day -1 until end of confinement [Day 8] of Periods 1 and 2); permitted during washout period and otherwise. Excessive consumption of caffeine- or xanthine-containing food or beverages not permitted from 48 hours prior to first planned administration of study intervention (see exclusion criterion 36). |
| Food and beverages containing grapefruit, grapefruit juice, grapefruit hybrids, star fruit, Seville orange, tangelo, pomelos, exotic citrus fruits. | Not permitted within 2 weeks prior to (re-)admission and during both treatment periods (Day -1 until end of confinement [Day 8] of Periods 1 and 2). See exclusion criterion 37. |
| Special diets | Preventing the subjects from eating the standard meals during the treatment periods, e.g. strict vegetarian or low caloric diet. |
| Caffeine, alcohol, and tobacco | |
| Smoking, use of tobacco / nicotine containing products (e.g., nicotine patch, chewing gum, or e-cigarettes) | Not permitted during the study. See inclusion criterion 6. |
| Alcohol | Not allowed from 48 hours prior to (re-) admission (Day -1) and during both treatment periods (Day 1 until end of confinement [Day 8] of Periods 1 and 2); permitted during washout period and otherwise. See exclusion criterion 35. |
| Activity | |
| Physical activity | Usual activities are permitted, but no strenuous physical exercise from 72 hours prior to admission until EOT. Subjects may participate in light recreational activities during hospitalization phase (e.g., watching television, reading). |
| Other restrictions | |
| Showering, bathing, swimming | Subjects are permitted to shower, bath, or swim 1 hour pre-dose or earlier, and after 3 hours post-dose or later. |
| Topical medication and cosmetics on the treatment site | Use of any topical medication, cosmetics, cream, ointments, lotions on the treatment site not permitted 2 weeks prior to enrollment through EOT visit (see exclusion criterion 27). |
| Exposure of the pre-defined application area to direct sunlight | To be avoided during both treatment periods (Day -1 to Day 8 of Periods 1 and 2). Permitted during washout period. |

continued

Table 5 (continued): Restrictions

| Other restrictions (continued) | |
|--|---|
| Solarium | Not permitted during both treatment periods (Day -1 to Day 8 of Periods 1 and 2). Not permitted during washout period. |
| Gel contact with eyes, nose, and mouth | To be avoided during the entire study. If gel contact occurs, rinse the affected area thoroughly with water. |
| Gel contact with hands | Subjects will be advised to wipe their hands e.g. with an absorbent paper and to wash them thoroughly after rubbing the gel into their knees, after each full administration of study intervention. The e.g. absorbent paper should be thrown in the trash after use. |
| Female subjects (WOCBP) only: Donation of eggs (ova, oocytes) for the purpose of reproduction. | Not permitted during trial participation and until 30 days after the last administration of study intervention. |

ED = early discontinuation; EOT = end of trial; WOCBP = woman/women of childbearing potential

5.4. Screen Failures

Screen failures are defined as subjects who consented to participate in the clinical study but are not subsequently randomly assigned to study intervention. A minimal set of screen failure information is required to ensure transparent reporting of screen failure subjects to meet the Consolidated Standards of Reporting Trials (CONSORT) publishing requirements and to respond to queries from regulatory authorities. Minimal information includes demography, screen failure details, eligibility criteria, and any SAE.

Individuals who do not meet the criteria for participation in this study (screen failure) may be rescreened up to 2 times (see Section 5.5). Rescreened subjects will be assigned a new screening number. Subjects who are rescreened are required to sign a new ICF (see Section 10.1).

5.5. Criteria for Temporarily Delaying Randomization

In case of abnormal results caused by intercurrent diseases, short-term treatable conditions, or other temporary health disorders (e.g., acute infection, iron deficiency, blood pressure outside defined range), the Investigator may decide to repeat the respective screening parameter(s). As a rule, up to 2 repetitions are acceptable.

6. Study Interventions and Concomitant Therapy

Study interventions are all pre-specified investigational and non-investigational medicinal products, medicinal devices, and other interventions (e.g., surgical, and behavioral) including marketed products, or placebo, or a combination of the same as per study plan, intended to be administered / applied to a study subject during the study conduct.

6.1. Study Interventions Administered

Table 6: Study Interventions

| Intervention Label | AMZ001 | Voltaren Emulgel |
|---------------------------------------|--|--|
| Intervention Name | AMZ001 gel | Voltaren Emulgel 1.16% Gel (Name of marketed reference product in Germany: Voltaren Schmerzgel 11,6 mg/g Gel) |
| Intervention Description | Transdermal hydroalcoholic gel formulation for skin administration | White to off white gel for skin administration |
| Type | Drug | Drug |
| Dose Formulation | Gel for topical administration | Gel for topical administration |
| Unit Dose Strength(s) | CCI [REDACTED] of AMZ001 gel contains CCI [REDACTED] of diclofenac sodium. | One (1) g of Voltaren Emulgel 1.16% Gel contains 11.6 mg of diclofenac diethylammonium, which corresponds to 10 mg diclofenac sodium. |
| Dosage Levels and Dosing Instructions | CCI [REDACTED] of AMZ001 will be applied once daily CCI [REDACTED] CCI [REDACTED] for 7 days, as per detailed application instruction. | CCI [REDACTED] of Voltaren Emulgel 1.16% Gel will be applied 4 times daily (CCI [REDACTED] at relative times 0h, 5h, 10h, 15h), for 7 days, as per detailed application instruction. |
| Route of Administration | Topical administration | Topical administration |
| Use | Experimental | Active comparator |
| Marketing Authorization Holder | NA | Haleon Germany GmbH 80258 Munich, Germany |
| IMP and NIMP/AxMP | IMP | IMP |

continued

Table 6 (continued): Study Interventions

| Intervention Label | AMZ001 | Voltaren Emulgel |
|--------------------------------|---|--|
| Sourcing | The Sponsor will provide Nuvisan GmbH with the medication, which will be released by the Sponsor QP according to Good Manufacturing Practice Annex 13 for use in the study. CTS Nuvisan will create a CoC for the labelling activities performed. | Nuvisan will source medication available on the local market. |
| Packaging and Labelling | Study intervention will be provided by the Sponsor in dispensing packages, measuring 1 mL per actuation. Each IMP dispenser will be labelled according to country requirement by Nuvisan. | Study intervention will be used as unchanged product with market authorization |

AxMP=auxiliary medicinal product, NA=not applicable, NIMP=non-investigational medicinal product; IMP=investigational medicinal product.

In each period, subjects will receive multiple topically applied doses of AMZ001 gel or Voltaren Emulgel 1,16% Gel from Day 1 to Day 7, as outlined in [Table 6](#) and in line with the detailed administration instructions.

Study interventions will be self-administered to both knees by the subject himself / herself under the supervision of a designated clinical site staff member for consistency in application and to ensure the correct amount is applied to each knee at the specified dose and frequency for 7 consecutive days. The subject will spread the gel directly to the pre-defined treatment area of approximately 500 cm² for AMZ001 and 400 cm² for Voltaren Emulgel 1.16% Gel, for each subject knee as per detailed application instructions. Further information on restrictions is provided in [Table 5](#). Further instructions for use will be provided in an IMP handling manual.

AMZ001 IMP dispensers and Voltaren Emulgel 1.16% Gel tubes will be weighed throughout the study before and after each administration of study intervention, as outlined in the SoA (Section [1.3](#)).

6.2. Preparation, Handling, Storage, and Accountability

1. The Sponsor will supply enough study intervention AMZ001 to Nuvisan Clinical Trial Supplies (CTS) Department.

2. Nuvisan will source the commercial reference product Voltaren Emulgel 1.16% Gel from the German market.
3. Nuvisan CTS Department will document the receipt of the study intervention AMZ001 and must confirm appropriate conditions (e.g., temperature) have been maintained during transit for all study intervention received and any discrepancies are reported and resolved before use of the study intervention AMZ001. Nuvisan CTS Department will be responsible for transfer to the site.
4. Study intervention AMZ001 will be packed and labelled study specifically by Nuvisan CTS Department before the clinical part of the study starts. QP release of clinical supplies will be performed by the Sponsor as per the German clinical study labelling requirements.
5. Only subjects enrolled in the study may receive study intervention and only authorized site staff may supply, prepare, or supervise the administration of study intervention. All study intervention must be stored in a secure, environmentally controlled, and monitored (manual or automated) area in accordance with the labelled storage conditions with access limited to the Investigator and authorized site staff.
6. All study intervention administrations will be performed in accordance with the product specifications under supervision of site staff authorized by the Principal Investigator.
7. The Investigator is responsible for study intervention accountability, reconciliation, and record maintenance (i.e., receipt, reconciliation, and final disposition records).
8. The number of unused study intervention will be documented by Nuvisan CTS Department. According to the provisions of the Sponsor the unused study intervention will be destroyed once the final reconciliation has been completed and the authorization for destruction has been received from the Sponsor.
9. Further guidance and information for the final disposition of unused study interventions are provided in the applicable manual.

6.3. Assignment to Study Intervention

| | |
|---|--|
| Subject identification and intervention assignment | 
After informed consent procedure, every subject is given a screening number.
 
Within the afternoon of Day -1 of Period 1 until pre-dose of Day 1 of Period 1, before any Day 1 procedures, subjects will be assigned a unique 3-digit randomization number in ascending numerical order. The number encodes the subject's assignment to one of the 2 arms of the study, according to the randomization list provided by Nuvisan CTS Department. Each subject will be dispensed study intervention, labelled with their unique randomization number throughout the study.
 
Replacement subjects of already randomized subjects prior to dosing will be assigned to the intervention as the original subject. Randomization number will be the number of the original subject plus 100. For example, the replacement for screening number 012 will receive the random number 112.
 |
|---|--|

Only subjects who comply with all eligibility criteria can be included into the study. Subjects will be assigned to randomization numbers in accordance with Nuvisan standard operational procedures (SOPs).

The Investigator will keep a record relating the subject identifiers (screening and random number) and the names of all subjects who have given their informed consent, to allow easy checking of data in subject files, when required. This record will also include the date of subject's enrolment and completion, as well as subjects who could not be randomly assigned to study intervention for whatever reason.

6.4. Blinding, Masking

The study will be performed in a non-blinded design.

6.5. Study Intervention Compliance

The administration of the study intervention will be performed in the clinical unit by qualified clinical professionals of the Investigator's team. Deviation(s) from the prescribed dosage regimen should be recorded in the case report form (CRF).

6.6. Dose Modification

No dose modifications are envisaged during this study.

6.7. Continued Access to Study Intervention after the End of the Study

As this is a study in healthy volunteers, no intervention is planned at the end of the study. If there are findings that are unclear in the final examination, a detailed assessment, a follow-up and, if necessary, specific medical treatment may be required.

6.8. Treatment of Overdose

For this study, any dose of study intervention greater than the protocol-defined dose will be considered an overdose.

The low systemic absorption of study interventions renders overdose very unlikely. However, according to the [SmPC](#) of Voltaren Emulgel 1.16% Gel, undesirable effects, similar to those observed following an overdose of diclofenac tablets, can be expected if Voltaren Emulgel 1.16% Gel is inadvertently ingested (e.g. 1 tube of 100g contains the equivalent of 1000 mg of diclofenac sodium).

Management of overdosage with NSAIDs essentially consists of supportive and symptomatic measures. There is no typical clinical picture resulting from Voltaren Emulgel 1.16% Gel overdosage. Supportive and symptomatic treatment should be given for complications such as hypotension, renal failure, convulsions, gastro- intestinal irritation, and respiratory depression; specific therapies such as forced diuresis, dialysis or hemoperfusion are probably of no help in eliminating NSAIDs due to their high rate of protein binding and extensive metabolism.

In the event of accidental ingestion, resulting in significant systemic adverse effects, general therapeutic measures normally adopted to treat poisoning with non- steroidal anti-inflammatory medicines should be used. The use of activated charcoal should be considered, especially within a short time (within one hour) of ingestion of a toxic dose (see [SmPC](#)).

According to the current [IB](#) of AMZ001, no incidents of overdose have been reported with AMZ001 (diclofenac sodium gel [\[CC\]](#)). Possible effects of overdose include those observed after an overdose of oral diclofenac. Symptoms following excessive ingestion of an oral NSAID may include lethargy, drowsiness, nausea, vomiting, and epigastric pain. In severe cases, GI bleeding, hypertension, acute renal failure, respiratory depression, coma, and anaphylaxis may occur.

The Sponsor does not recommend specific treatment for an overdose with AMZ001, and treatment should be symptomatic and supportive as appropriate.

In the event of an overdose, the Investigator should:

1. Evaluate the subject to determine, in consultation with the responsible PhV expert, if possible, whether study intervention should be interrupted or whether the dose should be reduced.
2. Closely monitor the subject for any AE/SAE and laboratory abnormalities until study intervention can no longer be detected systemically (at least 1 day).

3. If requested by the responsible PhV expert (determined on a case-by-case basis), obtain a plasma sample for PK analysis within 1 day from the date of the last dose of study intervention.
4. Document the quantity of the excess dose as well as the duration of the overdose in the CRF. Decisions regarding dose interruptions or modifications will be made by the Investigator in consultation with the Sponsor based on the clinical evaluation of the subject.

6.9. Prior and Concomitant Therapy

Any medication taken at or after the time of first study intervention, regardless of whether it had started prior to the study or not, is to be recorded as concomitant medication. Prior medications are defined as any medication taken which had been stopped prior to the first study intervention.

Subjects must abstain from taking prescription or non-prescription drugs (including vitamins and dietary or herbal supplements) within 2 weeks or 10 half-lives (whichever is longer) before the start of study intervention until completion of the EOT visit. Information on non-permitted prior or concomitant therapy including drugs and herbal remedies is provided in the list of exclusion criteria and meals and dietary restrictions. See Sections [5.2](#) and [Table 5](#) for further details.

In addition, subjects must abstain from using any topical medication, cosmetics, cream, ointments, lotions on the treatment site 2 weeks prior to enrollment through EOT visit, as indicated in the list of exclusion criteria (see Section [5.2](#) and [Table 5](#)).

Except when necessary to treat an AE, subjects are not allowed to use those medications, starting from the specified timepoints until completion of the study.

Paracetamol (acetaminophen) at doses of 500 mg (\leq 2 gram/day, if needed), is permitted for use any time during the study. Contraceptives as outlined in Section [10.4](#) are also permitted. Hormone replacement therapy is permitted, as long as the female subject is on stable treatment for at least 3 months and continues treatment throughout the study (see Section [5.2](#)).

Single intake of other medication is only permitted, if it is judged by the Investigator to have no clinical relevance and if it is not expected to confound the interpretation of the study results.

Other concomitant medication may be considered on a case-by-case basis to avoid immediate hazard to the subjects by the Investigator who may wish to consult with the Medical Monitor or Sponsor.

For any concomitant therapy used, the name of the drug, the reason for use, dates of administration including start and end dates and dosage information including dose and frequency will be recorded in the CRF. In consultation with the Sponsor, a decision may be taken by the Investigator to withdraw a subject from the study when other concomitant medication is required or has been taken without consulting the Investigator.

6.9.1. Rescue Medicine

Not applicable.

7. Discontinuation of Study Intervention and Subject Discontinuation/Withdrawal

7.1. Discontinuation of Study Intervention

In rare instances, it may be necessary for a subject to permanently discontinue study intervention. If study intervention is permanently discontinued, the subject will remain in the study. Safety, and tolerability data as well as PK data will be collected to the furthest possible extent and the subject will be asked to participate in the early discontinuation visit.

See the SoA (Section 1.3) for data to be collected at the time of discontinuation of study intervention and ED / EOT visit and for any further evaluations that need to be completed.

7.1.1. Discontinuation Criteria for Individual Subjects

The Investigator will withdraw a subject from receiving further study intervention in the following cases:

- Occurrence of an AE of severe severity in case of causal relationship to study intervention.
- Relevant signs or symptoms affecting subject safety. Any events that unacceptably endanger the safety of the subject.
- If, in the Investigator's opinion, continuation of the study would be harmful to the subject's well-being.
- Hypersensitivity reactions classified as severe.
- Impossibility to obtain blood samples in general.
- Abnormal blood pressure including hypotension defined as systolic <70 mmHg and/or diastolic <40 mmHg, or hypertension defined as systolic >160 mmHg and/or diastolic >110 mmHg (evaluated with the subject in supine position for a minimum of 5 minutes and confirmed by 2 repeat measurements). In case of repeat abnormal findings, see above, this should lead to direct study withdrawal.
- Creatinine >1.1xULN
- Use of nonpermitted concomitant medications. However, any medications considered necessary for the subject's wellbeing may be given at the discretion of the Investigator.
- Occurrence of pregnancy. See Section 8.4.5 and Section 10.4.

7.1.1.1. Liver Chemistry Stopping Criteria

Discontinuation of study intervention for abnormal liver tests is required by the Investigator when a subject meets one of the following conditions or if the Investigator believes that it is in best interest of the subject:

- Increase in ALT or AST ≥ 3 xULN and/or total bilirubin >2 xULN considered by the Investigator to be at least possibly related to the study intervention. ALT ≥ 3 xULN and bilirubin ≥ 2 x ULN ($>35\%$ direct bilirubin) has to be reported as SAE (refer to Section 10.5).

7.2. Subject Discontinuation / Withdrawal from the Study

7.2.1. Discontinuation / Withdrawal Criteria for Individual Subjects

- A subject may withdraw from the study at any time at their own request without giving reasons. The subject will not suffer any disadvantage as a result. A subject may be withdrawn at any time at the discretion of the Investigator for safety, behavioral, compliance, or administrative reasons. This is expected to be uncommon.
- At the time of discontinuing from the study, if possible, an early discontinuation visit should be conducted. See SoA in Section 1.3 for data to be collected at the time of study discontinuation and ED and for any further evaluations that need to be completed.
- The subject will be permanently discontinued from both the study intervention and the study at that time.
- If the subject withdraws consent for disclosure of future information, the Sponsor may retain and continue to use any data collected before such a withdrawal of consent.
- If a subject withdraws from the study, they may request destruction of any samples taken and not tested, and the Investigator must document this in the site study records.
- Subjects who discontinue may not re-enter the study.
- Depending on the timepoint of discontinuation, a withdrawn subject is referred to as either “screening failure” or “dropout” as specified in Sections 5.4 and Section 7.2.2.

The Investigator will withdraw a subject from the study in the following cases:

- Request by the subject to discontinue (withdrawal of consent).
- At the specific request of the Sponsor and in liaison with the Investigator (e.g., obvious non-compliance).
- Any clinically relevant symptom or sign which in the opinion of the Investigator and/or Sponsor warrants subject withdrawal.
- Impossibility to obtain samples.
- Positive results from pregnancy testing.
- Protocol deviation judged as significant by the Investigator, including non-compliance to the required study considerations (e.g., food/diet requirements).

- Depending on the timepoint of withdrawal, a withdrawn subject will be referred to as either “screening failure” or “dropout” as specified in Section 5.4 and Section 7.2.2.

7.2.2. Replacement of Subjects

A subject who discontinues the study prematurely for any reason is defined as a ‘dropout’ if the subject has already been randomly assigned to study intervention.

Dropouts will be replaced only if the number of subjects completing the study becomes less than 34 to ensure a total number of 26 evaluable subjects. For details regarding intervention assignment of replacement subjects, please refer to Section 6.3.

The data obtained from dropouts will be used in the evaluation to the largest possible extent.

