| 
 To assess the safety and local tolerability of CCI of AMZ001 (diclofenac sodium gel CCI) and CCI of Voltaren Emulgel 1.16% Gel (diclofenac diethylamine gel 1.16%). | 
 Number of subjects with TEAEs including SAEs Number of subjects with study intervention-related TEAEs Assess the skin irritation of each product |

Overall Design:

This study will be conducted in a single-center, randomized, open-label, 2-period crossover design. Healthy male and female subjects (18 to 65 years, inclusive) are eligible.

Brief Summary:

The main purpose of this study in healthy male and female subjects is to investigate the systemic bioavailability of **CCI** of AMZ001 applied once daily as **CCI** per knee on both knees compared to **CCI**, of Voltaren Emulgel 1.16% Gel applied 4 times daily as **CCI** per knee on both knees for 7 days.

Additionally, the PK profile, and the safety and local tolerability of AMZ001 gel and Voltaren Emulgel 1.16% Gel will be evaluated.

Study details include:

- The study duration will be approximately 9 weeks per subject, depending on the length of the screening- and wash-out periods.
- Two (2) study periods are planned in crossover design, with a wash-out period (WOP) of at least 21 days in-between.
- In each study period, subjects will self-administer AMZ001 gel OR Voltaren Emulgel 1.16% Gel under the supervision of a designated clinical site staff member:
 - One (1) dose [REDACTED] of AMZ001 will be applied once daily as [REDACTED] per knee on both knees.
 - OR
 - One (1) dose [REDACTED] of Voltaren Emulgel 1.16% Gel will be applied 4 times daily as [REDACTED] per knee on both knees.
- The intervention duration will be 7 days per period, i.e., from Day 1 to Day 7 of Periods 1 and 2.
- The screening examination will be performed within 21 to 2 days prior to the first administration of study intervention.
- Subjects will stay in-house for 9 days per study period. During the WOP, subjects will not be confined to the study site.
- The end of trial (EOT) visit will be performed in the morning of Day 8 of Period 2 and subjects will be discharged afterwards.

Number of Subjects:

A total of 34 subjects are intended to be randomized to study intervention, so that at least 26 subjects will be valid for pharmacokinetic (PK) evaluation of diclofenac.

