Subjects who prematurely discontinue the study after having been assigned to study intervention may be replaced if the number of valid subjects for PK becomes or is expected to become less than 26 subjects. Subjects who drop out prior to first administration of study intervention (early dropouts) may be replaced immediately.

Study Intervention Groups and Duration:

For each subject, the study will consist of an ambulatory screening visit (within 21 days to 2 days prior to the first administration of study intervention [until Day -2]), 2 in-house periods of 9 days each (Day -1 to Day 8 of Periods 1 and 2) and a wash-out period of at least 21 days.

In Periods 1 and 2, eligible subjects will be admitted to the study ward 1 day prior to administration of the study interventions (Day -1 of the respective study period).

From Day 1 to Day 7 of Periods 1 and 2, subjects will self-administer AMZ001 gel or Voltaren Emulgel 1.16% Gel under the supervision of a designated clinical site staff member in 1 of the following 2 dosing sequences:

Period 1

(Sequence 1) AMZ001 gel - **CCI** daily: 1 time daily **CCI** on each knee for 7 days

(Sequence 2) Voltaren Emulgel 1.16% Gel - **CCI** daily: 4 times daily **CCI** on each knee for 7 days

Period 2

(Sequence 1) Voltaren Emulgel 1.16% Gel - **CCI** daily: 4 times daily **CCI** on each knee for 7 days

(Sequence 2) AMZ001 gel - **CCI** daily: 1 time daily **CCI** on each knee for 7 days

Subjects will remain in-house for 9 days per study period (from Day -1 until discharge in the morning of Day 8) provided there are no medical objections. Periods 1 and 2 will be separated by a wash-out period of at least 21 days, during which the subjects will not be confined to the study site.

[figure not shown]
An end of trial (EOT) visit will be performed in the morning of Day 8 of Period 2 and subjects will be discharged afterwards.

The duration of study participation will be up to approximately 9 weeks per subject, depending on the length of the screening period (up to 21 days) and the length of the wash-out period (at least 21 days). For each subject, the study will end with the above-mentioned EOT visit.

Data Monitoring/Other Committee: No

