9.5. Sample Size Determination

It is planned to assign 34 subjects to study intervention to have at least 26 evaluable subjects completing the study. If deemed necessary to meet the target number of 26 evaluable subjects, dropouts may be replaced (refer to Section 7.2.2).

Based on the assumption (average CV of 3 historical studies), the intra-subject coefficient of variation (CV) was about 43%. A total of 26 evaluable subjects will achieve 80% power, that the 90% confidence interval (CI) is included in the pre-defined acceptance range of 0.7-1.43, which is deemed to be appropriate. The true ratio that was used in the sample size calculation was 1.05. Enough healthy adults will be screened to randomize approximately 34 subjects to ensure 26 evaluable subjects, assuming an approximate 20% dropout and non-evaluable rate.

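### Section 7.2.2 sets the replacement trigger at fewer than 34 completers, which is the number randomised; the synopsis and Section 9.5 set it at 26 for subjects who drop out after dosing

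*Protocol*

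**What the plan says.** Protocol Section 7.2.2 gives the rule as "Dropouts will be replaced only if the number of subjects completing the study becomes less than 34", followed by its purpose, "to ensure a total number of 26 evaluable subjects". It calls a subject who discontinues a dropout "if the subject has already been randomly assigned to study intervention", so the term covers undosed as well as dosed subjects.

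The synopsis (Section 1.1) states the plan as "A total of 34 subjects are intended to be randomized to study intervention, so that at least 26 subjects will be valid" for PK evaluation. Subjects who discontinue after assignment "may be replaced if the number of valid subjects for PK becomes or is expected to become less than 26 subjects". It adds a separate rule without a threshold: "Subjects who drop out prior to first administration of study intervention (early dropouts) may be replaced immediately".

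Section 9.5 says "If deemed necessary to meet the target number of 26 evaluable subjects, dropouts may be replaced" and refers to 7.2.2 for the rule. It explains the 34 as the number randomised "to ensure 26 evaluable subjects, assuming an approximate 20% dropout and non-evaluable rate". Section 4.1 also gives 26 as the minimum number of valid subjects. Section 4.4 counts a subject as having completed only after all phases of the study.

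**The concern.** The 34 in 7.2.2 is the number randomised, used where the number required at the end belongs. The 34 was chosen so that some subjects could be lost and 26 would still remain. A completer threshold of 34 leaves no room for any loss, so the allowance is counted twice. Since a completer must have finished both periods, the first dropout takes the count below 34 and the restriction in 7.2.2 restricts nothing.

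For subjects lost after dosing, the site therefore has two different triggers, and 9.5 sends the reader to the section with the wrong number. Subjects lost before first administration are not part of the conflict, because the synopsis allows their immediate replacement whatever the count.

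At stake is the number of healthy volunteers, who have no direct benefit, randomised and dosed beyond what the stated power needs. The effect estimate is not at risk, and extra subjects would raise power.

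**Working it through.** **Inputs.** From Section 9.5: intra-subject CV 43%, true ratio 1.05, acceptance range 0.70 to 1.43, 90% confidence interval (two one-sided tests at 5%), 80% power with 26 evaluable, 34 randomised, about 20% dropout and non-evaluable. From 7.2.2: trigger of 34 completers. From the synopsis: trigger of 26 subjects valid for PK.

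**1. Reproduce the plan's figures.** For a 2x2 crossover on the log scale:

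- Within-subject SD = √ln(1 + 0.43²) = 0.412.
- SE of the treatment difference = 0.412 × √(2/n), with n − 2 degrees of freedom. At n = 26 this is 0.114; at n = 34 it is 0.100.
- Exact power of the two one-sided tests:

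| Evaluable n | Power |
|---|---|
| 24 | 76.0% |
| 26 | 80.1% |
| 34 | 90.6% |

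So 26 is the smallest even number that reaches 80%, as stated. Inflating for 20% loss gives 26 / 0.80 = 32.5, rounded up to 33; the plan's 34 agrees within one subject. Hence 26 is the requirement, and 34 is the requirement plus the allowance.

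**2. When each trigger is met, starting from 34.**

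- Section 7.2.2: 34 − 1 = 33 completers, below 34 at the 1st loss.
- Synopsis: 34 − 8 = 26 is still enough; 34 − 9 = 25 is below 26, so the 9th loss.

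The two rules give different answers from the 1st to the 8th loss.

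**3. How often each is met.** The protocol does not split its 20% into dropout and non-evaluable, so the post-dose dropout rate p is an assumption, taken as 5%, 10% and 20%. With losses Binomial(34, p):

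| p | At least 1 loss | At least 9 losses |
|---|---|---|
| 5% | 82.5% | <0.1% |
| 10% | 97.2% | 0.5% |
| 20% | 99.95% | 22.7% |

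**4. Number randomised under each rule.**

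- Keep 34 completers: 34 + NegBin(34, 1 − p), with mean 34 / (1 − p).
- Start with 34 and replace only to keep 26: max(34, 26 + NegBin(26, 1 − p)).

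| p | Keep 34: mean (95th percentile) | Keep 26: mean (95th percentile) | Difference in means |
|---|---|---|---|
| 5% | 35.8 (38) | 34.0 (34) | 1.8 |
| 10% | 37.8 (41) | 34.0 (34) | 3.8 |
| 20% | 42.5 (48) | 34.6 (38) | 7.9 |

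The means are not upper bounds: at p = 20%, keeping 34 completers would take more than 43 randomised subjects with probability 35%.

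**The case against.** The strongest reply is that the condition in 7.2.2 is a necessary one. Whenever dropouts bring evaluable subjects below 26, completers are already below 34, so a site that follows the synopsis never breaches 7.2.2. On that reading the number is empty rather than in conflict, and the purpose clause in the same sentence points to 26. This stands in part: read by its purpose, 7.2.2 requires no extra dosing. But the sentence says dropouts *will* be replaced where the synopsis and 9.5 say *may*, which invites reading it as a trigger. A threshold that excludes nothing is also badly set.

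The 20% row is an upper scenario. The stated rate includes non-evaluable subjects, and a completer who is non-evaluable does not lower the completer count. With an assumed split of 10% dropout and 10% non-evaluable, the comparison is about 37.8 against 34.6, or about 3 extra subjects. That stands, and it is why a range is shown.

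The limit to dosed subjects is an inference from the separate synopsis sentence on early dropouts. Section 9.5 makes no such distinction and gives 26 as a target. The inference is fair, and a rule covering all dropouts covers dosed ones too.

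**Conclusion.** The point holds. Section 7.2.2 uses 34, the number randomised, as its replacement threshold; the synopsis and Section 9.5 use 26 and Section 4.1 gives 26 as the minimum, and no other section resolves the difference. For dosed dropouts the triggers are eight losses apart. The practical size depends on the reading: nothing if the purpose clause governs, and on average about 2 to 8 additional healthy volunteers if 7.2.2 is taken literally, over assumed dropout rates of 5% to 20%. The sample size, the power statement and the validity of the analysis are unaffected. It should be corrected, because the site acts on this number during the study.

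**What to change.** In Section 7.2.2:

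- Replace the threshold of 34 completers with 26, counting subjects who have, or are expected to have, a valid Day 7 AUC0-24 in both periods. The primary ANOVA in Section 9.3.3 uses only subjects valid in both periods, whereas the PK Set in Section 9.2 requires only one completed period, so a count of subjects valid for PK would be ambiguous on its own. Final exclusions are decided at the data review meeting, so during enrolment the count has to rest on expectation.
- Limit that sentence to dropouts after first administration.
- Add the synopsis rule that subjects who drop out before first administration may be replaced immediately. This is needed because 7.2.2 calls every randomised subject who discontinues a dropout.

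The cost is one sentence changed and one added. The 34 randomised, the 26 evaluable, the power and the analysis stay as they are.

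While editing, note that 7.2.2 refers to Section 6.3 for the assignment of replacements, and 6.3 covers only replacement before dosing. That gap exists with or without this change.
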